1.2 Schedule of Activities (SoA)

Table 1 Schedule of Activities

Procedures	Non-PSG Screening V1	Screening/ Baseline PSG V2	Dosing Period								EoS Call	
			ATO 40 3d, ATO 80 4d		ATO 40/DRO 2.5		ATO 80/DRO 5		ATO 80/DRO 10			
			At home dosing	V3 PSG	At home dosing	V4	At home dosing	V5	At home dosing	PSG V6		
Day ¹	-21 to -1		1 - 7 ± 1	7 ± 1	8-14 ± 2	14 ± 2	15 – 21 ± 2	21 ± 2	21-28 ± 2	28 ± 2	42 ± 2	
Informed consent	X											
Demography	X											
Physical exam	X											
Medical history	X											
Pregnancy test ²	X											
Clinical laboratory testing	X											
12 Lead ECG	X											
PSG		X ³		X				X		X		
Study drug dispense/return		X		X		X		X		X		
HS study treatment ⁴			↔	↔	↔	↔	↔	↔	↔	↔		
PGI-S, PROMIS sleep impairment, PROMIS sleep disturbance, PROMIS fatigue, DSST, VOLT, PVT ⁵		X		X				X		X		
Vital signs ⁶	X	X		X		X		X		X		
AE/SAE monitoring ⁷			↔	↔	↔	↔	↔	↔	↔	↔	↔	
Prior/concomitant medication			↔	↔	↔	↔	↔	↔	↔	↔	↔	

Abbreviations: AE = adverse event; ATO = atomoxetine; DRO = dronabinol; DSST = Digit symbol substitution test; ECG = electrocardiogram; HS = Hora Somni; PGI-S = patient global impression of severity of OSA; PSG = polysomnography; SAE = serious adverse event; SAQI = Sleep Apnea Quality of Life Index; WOCBP = women of childbearing potential; PROMIS = Patient Reported Outcomes Measurement Information System; PVT = psychomotor vigilance test; VOLT = visual object learning task

¹Study days shown represent case with no use of ± window days; study days shift cumulatively if window days are used

² WOCBP only

³ On a case-by-case basis with agreement of Sponsor a PSG conducted at the site within 3 months may be used instead of the Screening PSG

⁴ Study medication administered at lights out; dose on PSG nights is from supply dispensed to the participant if available, but can be provided from separate site supply.

⁵ Administered at similar time on morning of each PSG visit

⁶ Vital signs include seated blood pressure in triplicate, pulse, respiratory rate; vital signs on PSG nights taken morning after PSG.

⁷ Site contacts participant by telephone mid-week of each at-home dosing period for safety evaluation and reminder of study activities

2 Introduction

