4.1 Overall Design

The SEED study is an open-label, 4 consecutive period dose-escalation study of combinations of atomoxetine and dronabinol in participants with moderate to severe OSA. Participants will undergo initial pre-screening to determine potential study eligibility. Participants selected for further screening should either have a previous history of OSA of a severity consistent with enrollment criteria or be at high risk (e.g. as assessed by STOP-Bang Questionnaire score). Only participants who meet all non-PSG enrollment criteria at Visit 1 are eligible for a screening PSG. On a case by case basis and with agreement of the Sponsor a PSG conducted at the site within 3 months may be used instead of the Screening PSG.

Participants who meet all enrollment criteria will receive an escalating dose of atomoxetine the first week: 3 days of atomoxetine 40 mg followed by 4 days of atomoxetine 80 mg. Participants will then receive escalating dose combinations of atomoxetine and dronabinol for the next 3 weeks. The weekly dose schedule is as follows:

- Week 1: atomoxetine 40 mg x 3 days, then 80 mg x 4 days
- Week 2: atomoxetine 40 mg/dronabinol 2.5 mg
- Week 3: atomoxetine 80 mg/dronabinol 5 mg
- Week 4: atomoxetine 80 mg/dronabinol 10 mg

Dose escalation will be based on safety and tolerability, as assessed at weekly clinic visits and by telephone contact with participants mid-week of each at-home dosing period. Patients who do not tolerate dose escalation will discontinue dosing.

Three on-drug PSGs will be conducted on the final night of the following dosing periods:

- 1st week, dosing atomoxetine 80 mg alone
- 3rd week, dosing atomoxetine 80 mg/dronabinol 5 mg
- 4th week, dosing atomoxetine 80 mg/dronabinol 10 mg

Study drug for Week 1 is dispensed to participants at Visit 2.. Any unused Week 1 study drug is returned at Visit 3. Similarly, study drug for Week 2, 3, and 4 is dispensed at Visits 3, 4 and 5, and unused study drug similarly returned at the subsequent visit.

Dosing of the study treatment will occur each night at the participant's usual bedtime, both during at-home nights and Visit 3, Visit 5 and Visit 6 PSG nights. Study drug dose on PSG nights

[figure not shown]
is from the supply dispensed to the participant if available, but can be provided from separate site supply.

The morning of each PSG the PGI-S, PROMIS assessments, DSST, VOLT and PVT will be administered.

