5.1 Inclusion Criteria

Age and Sex

1. 25 to 65 years of age, inclusive, at the Screening Visit.

Disease Measures

2. AHI 10 to 50 (hypopneas defined by 4% oxygen desaturation)
3. $\leq 25\%$ of apneas are central or mixed apneas at V2 baseline PSG

Weight

4. BMI between 18.5 and 40.0 kg/m², inclusive, at the pre-PSG visit.

Male participants:

5. If male and sexually active with female partner(s) of childbearing potential, participant must agree, from Study Day 1 through 1 week after the last dose of study drug, to practice

the protocol specified contraception (see Appendix 4: Contraceptive Guidance and Collection of Pregnancy Information).

Female participants:

6. If a woman of childbearing potential (WOCBP), the participant must agree, from Study Day 1 through 1 week after the last dose of study drug, to practice the protocol specified contraception (See Appendix 4: Contraceptive Guidance and Collection of Pregnancy Information). All WOCBP must have negative result of a serum pregnancy test performed at screening.
7. If female and of non-childbearing potential, the participant must be either postmenopausal (defined as age ≥ 55 years with no menses for 12 or more months without an alternative medical cause) or permanently surgically sterile (bilateral oophorectomy, bilateral salpingectomy or hysterectomy).

Informed Consent

8. Participant voluntarily agrees to participate in this study and signs an Institutional Review Board (IRB)-approved informed consent prior to performing any of the Screening Visit procedures.
9. Participant must be able to understand the nature of the study and must have the opportunity to have any questions answered.

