5.2 Exclusion Criteria

Participants are excluded from the study if any of the following criteria apply:

Medical Conditions

1. History of clinically significant sleep disorder other than OSA.
2. Clinically significant craniofacial malformation.
3. Clinically significant cardiac disease (e.g., rhythm disturbances, coronary artery disease or cardiac failure) or hypertension requiring more than 2 medications for control (combination medications are considered as 1 medication for this purpose).
4. Clinically significant neurological disorder, including epilepsy/convulsions.
5. History of schizophrenia, schizoaffective disorder or bipolar disorder according to Diagnostic and Statistical Manual of Mental Disorders-5 (DSM-5) or International Classification of Disease tenth edition criteria.

6. History of attempted suicide within 1 year prior to screening, or current suicidal ideation.
7. Medically unexplained positive screen for drugs of abuse or history of substance use disorder as defined in DSM-V within 24 months prior to Screening Visit.
8. A significant illness or infection requiring medical treatment in the past 30 days.
9. Clinically significant cognitive dysfunction as determined by investigator.
10. Women who are pregnant or nursing.

Prior/Concomitant Therapy

11. History of using devices for OSA treatment, including CPAP, oral or nasal devices, or positional devices, may enroll as long as the devices have not been used for at least 2 weeks prior to first study visit and are not used during participation in the study.
12. History of chronic oxygen therapy.
13. Use of medications from the list of disallowed concomitant medications.
14. Treatment with strong cytochrome P450 3A4 (CYP3A4) inhibitors, strong cytochrome P450 2D6 (CYP2D6) inhibitors, or monoamine oxidase inhibitors (MAOI) within 14 days of the start of treatment, or concomitant with treatment.

Prior/Concurrent Clinical Study Experience

15. Use of another investigational agent within 30 days or 5 half-lives, whichever is longer, prior to dosing.

Diagnostic Assessments

16. Hepatic transaminases >2X the upper limit of normal (ULN), total bilirubin >1.5X ULN (unless confirmed Gilbert syndrome), estimated glomerular filtration rate < 60 ml/min.
17. PLM arousal index >20

Other Exclusions

18. <5 hours typical sleep duration.
19. ESS > 18
20. Night- or shift-work sleep schedule which causes the major sleep period to be during the day.

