9.2 Appendix 2: Clinical Laboratory Tests

- The tests detailed in Table 2 will be performed by local laboratory.
- Laboratory testing is performed non-fasting.
- Additional tests may be performed at any time during the study as determined necessary by the Investigator or required by local regulations.

Table 2: Protocol-Required Safety Laboratory Assessments

Laboratory Assessments	Parameters		
Hematology	Hematocrit Hemoglobin Platelet Count RBC Count	RBC Indices	WBC count with Differential

Serum Chemistry	Albumin	ALT
	BUN	AST
	Creatinine	Alkaline phosphatase
	Potassium	Calcium
	Sodium	Glucose
	Bilirubin	Total cholesterol
	Total Protein	Chloride
	Uric acid	Bicarbonate
Other Tests	
• Urinalysis• HbA1c (Screening Visit only)• Serum hCG pregnancy test at screening. Additional testing may be performed if needed in WOCBP.• Urine test of drugs of abuse (marijuana, cocaine, amphetamine, methamphetamine, opiates, phencyclidine)	

Abbreviations: ALT = alanine aminotransferase; AST = aspartate aminotransferase; BUN = blood urea nitrogen; HbA1c = hemoglobin A1c (glycated hemoglobin); hCG = human chorionic gonadotropin; RBC = red blood cell count; WBC= white blood cell; WOCBP = women of childbearing potential.

Investigators must document their review of each laboratory safety report.

9.3 Appendix 3: Adverse Events: Definitions and Procedures for Recording, Evaluating, Follow-up, and Reporting

Definition of AE

AE Definition

• An AE is any untoward medical occurrence in a participant or clinical study participant, temporally associated with the use of a study treatment, whether or not considered related to the medicinal product.• NOTE: An AE can therefore be any unfavorable and unintended sign (including an abnormal laboratory finding), symptom, or disease (new or exacerbated) temporally associated with the use of a study treatment.

Events Meeting the AE Definition

• Any abnormal laboratory test results (hematology, clinical chemistry, or urinalysis) or other safety assessments (e.g., ECG, radiological scans, vital signs measurements), including those that worsen from baseline, considered clinically significant in the medical and scientific judgment of the Investigator (i.e., not related to progression of underlying disease).

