9.4 Appendix 4: Contraceptive Guidance and Collection of Pregnancy Information

Definitions

WOCBP

A woman is considered fertile following menarche and until becoming post-menopausal unless permanently sterile (see below).

Women in the following categories are not considered WOCBP:

1. Premenarchal
2. Premenopausal female with one of the following:
 - Documented hysterectomy
 - Documented bilateral salpingectomy

- Documented bilateral oophorectomy

NOTE: Documentation can come from the site personnel's review of the participant's medical records, medical examination, or medical history interview.

3. Post-menopausal female

- A post-menopausal state is defined as no menses for 12 months without an alternative medical cause. A high follicle-stimulating hormone (FSH) level in the post-menopausal range may be used to confirm a post-menopausal state in women not using hormonal contraception or hormonal replacement therapy (HRT). However, in the absence of 12 months of amenorrhea, a single FSH measurement is insufficient.
- Females on HRT and whose menopausal status is in doubt will be required to use one of the non-estrogen hormonal highly effective contraception methods if they wish to continue their HRT during the study. Otherwise, they must discontinue HRT to allow confirmation of post-menopausal status before study enrollment.

Contraception Guidance:

Male Participants:

Male participants with female partners of childbearing potential are eligible to participate if they agree to ONE of the following during the protocol-defined time frame:

- Are abstinent from penile-vaginal intercourse as their usual and preferred lifestyle (abstinent on a long-term and persistent basis) and agree to remain abstinent.
- Agree to use a contraceptive method with a failure rate of <1% per year as described in the table below when having penile-vaginal intercourse with a WOCBP who is not currently pregnant.

In addition, male participants must refrain from donating sperm for the duration of the study and for 3 months after the last dose of study treatment.

Male participants with a pregnant or breastfeeding partner must agree to remain abstinent from penile-vaginal intercourse or to use a male condom during each episode of penile penetration during the protocol-defined time frame.

Female Participants

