Female participants of childbearing potential are eligible to participate if they agree to use a highly effective method of contraception consistently and correctly as described in the table below.

Highly Effective Contraceptive Methods That Are User Dependent¹ Failure rate of <1% per year when used consistently and correctly.
Combined (estrogen- and progestin-containing) hormonal contraception associated with inhibition of ovulation ² 
• Oral• Intravaginal• Transdermal
Progestogen-only hormonal contraception associated with inhibition of ovulation 
• Oral• Injectable
Highly Effective Contraceptive Methods That Are User Independent¹
Implantable progestogen-only hormonal contraception associated with inhibition of ovulation 
• IUD• Intrauterine hormone-releasing system (IUS)• Bilateral tubal occlusion
Vasectomized partner
A vasectomized partner is a highly effective contraception method provided that the partner is the sole male sexual partner of the WOCBP and the absence of sperm has been confirmed. If not, an additional highly effective method of contraception should be used.
Sexual abstinence
Sexual abstinence is considered a highly effective method only if defined as refraining from heterosexual intercourse during the entire period of risk associated with the study treatment. The reliability of sexual abstinence needs to be evaluated in relation to the duration of the study and the preferred and usual lifestyle of the participant.

NOTES:

1 Typical use failure rates may differ from those when used consistently and correctly. Use should be consistent with local regulations regarding the use of contraceptive methods for participants participating in clinical studies.

Pregnancy Testing

- WOCBP should only be included after a confirmed menstrual period and a negative highly sensitive serum pregnancy test.
- Pregnancy testing will be performed whenever a menstrual cycle is missed or when pregnancy is otherwise suspected.

Collection of Pregnancy Information:

Female participants who become pregnant

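### Contraception for women of childbearing potential is required only from Study Day 1, but the one scheduled pregnancy test falls 1 to 21 days earlier

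*Combined protocol and SAP*

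**What the plan says.** Section 5.1, inclusion 6, sets the contraception period for women: "If a woman of childbearing potential (WOCBP), the participant must agree, from Study Day 1 through 1 week after the last dose" of study drug. It points to Appendix 4 for the methods and adds: "All WOCBP must have negative result of a serum pregnancy test performed at screening".

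The Schedule of Activities (Table 1) marks one pregnancy test, for WOCBP only, at Visit 1. The screening window is Day -21 to -1. No test is marked at Visit 2 or any later visit. Appendix 2 (Table 2) agrees: "Serum hCG pregnancy test at screening. Additional testing may be performed if needed in WOCBP".

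Under section 4.1, only participants who meet all non-PSG criteria at Visit 1 go on to the screening PSG at Visit 2, and "Study drug for Week 1 is dispensed to participants at Visit 2".

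Appendix 4 says: "Female participants of childbearing potential are eligible to participate if they agree to use a highly effective method of contraception consistently and correctly". It gives no start date. It also asks for a confirmed menstrual period before inclusion, without tying it to Visit 1 or Day 1, and calls for a test when a cycle is missed or pregnancy is suspected. Exclusion 10 bars "Women who are pregnant or nursing". Exclusion 23 bars women unwilling to use the specified contraception and is also undated. A participant who becomes pregnant is withdrawn.

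**The concern.** A negative test shows only that pregnancy was not detectable on the day of the sample. It protects the first dose only if conception is prevented from then on, or if a further test is done before dosing. The schedule contains no such test, and the one dated contraception rule begins on the first dosing day. A woman who follows inclusion 6 exactly as dated could therefore conceive after her qualifying test and enter dosing pregnant, which exclusion 10 is meant to prevent.

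At stake is early-pregnancy exposure to atomoxetine, and possibly dronabinol, until a missed cycle prompts a test.

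**Working it through.** **Inputs from the protocol.** Visit 1 test between Day -21 and Day -1 (Table 1). Contraception from Day 1 (inclusion 6). One dose each night from Day 1 (section 4.1). Week 1 is atomoxetine alone (40 mg for 3 days, 80 mg for 4), Week 2 is 40 mg/2.5 mg, and Week 3 is 80 mg/5 mg. There is no Day 0, and visit-window days are not used.

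**Assumption, not in the documents.** L = days from conception to missed menses, taken as 14 and varied from 10 to 16.

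**Step 1: the interval.** From Day -21 to Day 1 is 21 days; from Day -1 to Day 1 is 1 day. The upper end agrees with the synopsis, which allows up to 3 weeks for screening.

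**Step 2: doses before a missed cycle.** Let d = days from conception to Day 1, so Day -1 is d = 1. Doses = max(0, L - d).

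| Conception | L = 10 | L = 12 | L = 14 | L = 16 |
|---|---|---|---|---|
| Day -1 (d = 1) | 9 | 11 | 13 | 15 |
| Day -7 (d = 7) | 3 | 5 | 7 | 9 |
| Day -20 (d = 20) | 0 | 0 | 0 | 0 |

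At L = 14 and d = 1, menses are missed on Day 14, after doses on Days 1 to 13: 7 of atomoxetine alone and 6 of 40 mg/2.5 mg. At L = 16 the fifteenth dose is the first of 80 mg/5 mg. Irregular cycles or late recognition would add doses.

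**Step 3: can this happen with the Appendix 4 conditions met?** Take a 28-day cycle with ovulation 14 days before the next menses. If menses begin on the day of Visit 1 at Day -21, ovulation falls on Day -7 and the next menses are due on Day 8, after 7 doses. If menses and Visit 1 fall on Day -15, ovulation falls on Day -1 and menses are due on Day 14, after 13 doses. In both cases the confirmed period and the negative test are in order.

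**Step 4: what an earlier start date leaves.** Suppose contraception starts at the Visit 1 test, g days before Day 1, and conception occurred 1 day before Visit 1, too early to detect. Doses = max(0, L - 1 - g). With L = 14, g = 1 gives 12, g = 7 gives 6, and g = 13 or more gives 0. The change removes the interval after the test but not conceptions just before it.

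**The case against.** Day 1 is a coherent choice because it ties contraception to exposure. The methods listed in Appendix 4 include no barrier method, and most are already in place before a woman enters: an IUD, implant, tubal occlusion, ovulation-inhibiting hormones, a vasectomized partner, or abstinence as usual lifestyle. Consistent and correct hormonal use on Day 1 arguably implies starting earlier. Before dosing there are a confirmed period and a serum test. Once dosing starts there are clinic visits each week, and "Site contacts participant by telephone mid-week of each at-home dosing period for safety evaluation and reminder of study activities". Testing is mandatory on a missed cycle or suspicion, and extra testing is allowed.

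Much of this stands. It narrows the exposed group mainly to women who first start a method on Day 1, and it makes the probability low. It does not close the gap: none of these provisions requires contraception or a test between Visit 1 and the first dose, and the missed-cycle trigger acts only after the doses counted above.

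A reader might also infer that section 5.1 and Appendix 4 contradict each other, because the male text in Appendix 4 carries a time limit ("are eligible to participate if they agree to ONE of the following during the protocol-defined time frame") and the female text does not. The documents do not support that. Inclusion 6 supplies the dates and sends the reader to the appendix for the methods. The female text is undated, not in conflict.

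**Conclusion.** The point holds as a minor participant-safety gap. For 1 to 21 days after the qualifying test, no dated rule requires contraception and no test is scheduled before the first dose. This rests on the text alone. The dose counts rest on the assumed lag: about 13 for a conception on Day -1 (9 to 15 for lags of 10 to 16 days) and about 7 for one on Day -7.

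Three stronger readings should be resisted:

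- Thirteen doses is not a ceiling. It is the result for one conception day and one assumed lag.
- Not every WOCBP is exposed, since those already using a listed method are in practice covered. The documents give no expected number of WOCBP among the 15 participants.
- A repeat test at Visit 2 would not reliably catch what an earlier start date leaves. In the 12-dose case Visit 1 is on Day -1, so Visit 2 could be no later than that day and would face the same undetectable conception.

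Sample size, endpoints and analysis are unaffected.

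**What to change.** In inclusion 6, for WOCBP, replace the Study Day 1 start with the date of the screening pregnancy test. Put the same start date in the female text of Appendix 4 and in any matching consent text (the consent pages were not available for review). Inclusion 5, for men, can stay at Day 1.

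The change adds no visit, sample or procedure. Its cost is that WOCBP commit to contraception up to 3 weeks earlier. The benefit is largest when Visit 1 is well before Day 1 and small when Visit 1 is on Day -1. It does not detect a conception just before Visit 1.

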5.2 Exclusion Criteria

Participants are excluded from the study if any of the following criteria apply:

Medical Conditions

1. History of clinically significant sleep disorder other than OSA.
2. Clinically significant craniofacial malformation.
3. Clinically significant cardiac disease (e.g., rhythm disturbances, coronary artery disease or cardiac failure) or hypertension requiring more than 2 medications for control (combination medications are considered as 1 medication for this purpose).
4. Clinically significant neurological disorder, including epilepsy/convulsions.
5. History of schizophrenia, schizoaffective disorder or bipolar disorder according to Diagnostic and Statistical Manual of Mental Disorders-5 (DSM-5) or International Classification of Disease tenth edition criteria.

6. History of attempted suicide within 1 year prior to screening, or current suicidal ideation.
7. Medically unexplained positive screen for drugs of abuse or history of substance use disorder as defined in DSM-V within 24 months prior to Screening Visit.
8. A significant illness or infection requiring medical treatment in the past 30 days.
9. Clinically significant cognitive dysfunction as determined by investigator.
10. Women who are pregnant or nursing.

Prior/Concomitant Therapy

11. History of using devices for OSA treatment, including CPAP, oral or nasal devices, or positional devices, may enroll as long as the devices have not been used for at least 2 weeks prior to first study visit and are not used during participation in the study.
12. History of chronic oxygen therapy.
13. Use of medications from the list of disallowed concomitant medications.
14. Treatment with strong cytochrome P450 3A4 (CYP3A4) inhibitors, strong cytochrome P450 2D6 (CYP2D6) inhibitors, or monoamine oxidase inhibitors (MAOI) within 14 days of the start of treatment, or concomitant with treatment.

Prior/Concurrent Clinical Study Experience

15. Use of another investigational agent within 30 days or 5 half-lives, whichever is longer, prior to dosing.

Diagnostic Assessments

16. Hepatic transaminases >2X the upper limit of normal (ULN), total bilirubin >1.5X ULN (unless confirmed Gilbert syndrome), estimated glomerular filtration rate < 60 ml/min.
17. PLM arousal index >20

Other Exclusions

18. <5 hours typical sleep duration.
19. ESS > 18
20. Night- or shift-work sleep schedule which causes the major sleep period to be during the day.
21. Employment as a commercial driver or operator of heavy or hazardous equipment.

22. Typically smoking more than 10 cigarettes or 2 cigars per day, or inability to abstain from smoking during overnight PSG visits.
23. Unwilling to use specified contraception.
24. History of regular alcohol consumption of more than 14 standard units per week (males) or more than 7 standard units per week (females), or unwillingness to limit alcohol consumption to no greater than 2 units/day (males), 1 unit per day (females), not to be consumed within 3 hours of bedtime or on PSG nights.
25. Unwilling to limit during the study period caffeinated beverage intake (e.g., coffee, cola, tea) to 400 mg/day or less of caffeine, not to be used within 3 hours of bedtime.
26. Any condition that in the investigator's opinion would present an unreasonable risk to the participant, or which would interfere with their participation in the study or confound study interpretation.
27. Participant considered by the investigator, for any reason, an unsuitable candidate to receive atomoxetine and/or dronabinol or unable or unlikely to understand or comply with the dosing schedule or study evaluations.

